7.3 Secondary Efficacy Outcomes

Availability of the secondary outcomes will first be summarized by treatment arm and visit. Due to each secondary outcome having numerous measures associated with it (e.g., the OCT outcome can be measured by looking at macular thickness (central, pericentral and/or peripheral), macular volume, average macular thickness, presence of CME and/or subretinal fluid, integrity of photoreceptor layer, etc.), outcome measures thought to be of most importance were chosen by the Study Chair prior to any knowledge of treatment assignment. Using this pre-selected list of outcome measures, the following strategy will be used to analyze each continuous outcome.

- 1. Summary table of **descriptive** statistics broken down by treatment arm, Treatment Period and visit for change from baseline in the outcome measure. For VA and microperimetry, the summary table will also include the outcome measure on the original scale.
- 2. Analysis of **treatment effect** of cellular vs sham therapy during Treatment Period 1 (as described in Section 7.3.1.1) for the outcome measure on the original scale and change from baseline.
- 3. Analysis of **effect of cellular treatment over time** (as described in Section 7.3.1.2) for the outcome measure on the original scale and change from baseline.

For those outcomes that are categorical, a summary table of counts and frequencies will be provided, with any other planned analyses described within the relevant section.

These analyses will be conducted to gauge any changes in the outcome measures that could be attributed to the cellular therapy and to differentiate these changes from non-treatment factors (i.e., natural course of the condition, learning or placebo effects or testing variations). Graphical measures will be used to summarize and display trends over time. A (modified) intent-to-treat approach will be followed in which all participants who were randomized *and received the first injection* (cellular or sham) will be included in the analysis and analyzed in the arm to which they were randomized.

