Based on the observations of the preliminary phase 1 clinical trial, we anticipate any improvement in visual function associated with study cell therapy to occur within 3 months of cell therapy and for any effect to be sustained over time (but not increasing over time).⁵ Due to small sample sizes, it is recognized that there is limited power to detect differences (Appendix), but trends may be identified that would encourage future trials of this treatment, provided no safety concerns are found. Significance testing will use 2-sided tests with alpha=0.05. No adjustment for multiple comparisons will be made as these are purely exploratory analyses for hypothesis generation.

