7.3.1 Secondary Efficacy Outcome Analysis Methods

7.3.1.1 Treatment Effect of Cellular vs Sham Therapy During Treatment Period 1

Comparisons between the two treatment arms will be performed at 1, 3, and 6 months after the first treatment is administered as a method of exploring the differences between cellular and sham therapies. An independent t-test will be used to analyze the treatment effect for each continuous outcome measure on the original scale and change from baseline.

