7.3.2.1 Changes in Visual Acuity

Best corrected visual acuity (BCVA) of the study eye will be obtained at all scheduled study visits by a certified visual acuity examiner using ETDRS visual acuity chart and refraction. Table 3 outlines the outcome analyses that will be performed for visual acuity.

Table 3: Visual Acuity Outcomes				
Outcome Measure	Parameter	Timepoints	Analyses	
ETDRS Visual Acuity	Mean, mean change	All visits	Descriptive	
Letter Score	from baseline	1, 3 and 6 months following Treatment 1	Treatment effect	
		1, 3 and 6 months post- cellular therapy in both arms; 12 months post-cellular therapy in immediate cell/deferred sham arm	Effect of cellular therapy over time	
ETDRS Visual Acuity Improvement and Losses	Categorical change: Decrease by ≥ 10 letters/within 9 letters/improve by ≥ 10 letters; Decrease by ≥ 15 letters/within 14 letters/improve by ≥ 15 letters	All visits	Descriptive	

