7.3.2.3 Changes in OCT/OCTA

As a secondary outcome measure and a measure of change in macular morphology, OCT image analysis will be performed. Table 5 outlines the outcome analyses that will be performed for OCT/OCTA. Categorical versions of continuous variables may also be explored.

Table 5: OCT/OCTA Outcomes					
Modality	Outcome Measure	Parameter	Timepoints	Analyses	
ОСТ	Macular Thickness by ETDRS zone	Mean change from baseline	All visits	Descriptive	
	Macular thickness in ETDRS Zone 1 (Central)	Mean change from baseline	1, 3 and 6 months following Treatment 1	Treatment effect for central macular thickness	
			1, 3 and 6 months post-cellular therapy in both arms; 12 months post-cellular therapy in immediate cell/deferred sham arm	Effect of cellular therapy over time for central macular thickness	
	Macular Volume	Mean change from	All visits	Descriptive	
		paseline	1, 3 and 6 months following Treatment 1	Treatment effect	

Table 5: OCT/OCTA Outcomes				
Modality	Outcome Measure	Parameter	Timepoints	Analyses
			1, 3 and 6 months post-cellular therapy in both arms; 12 months post-cellular therapy in immediate cell/deferred sham arm	Effect of cellular therapy over time
	Average Macular Thickness	Mean change from baseline	All visits	Descriptive
	Presence of CME	Count, percentage, change from baseline	All visits	Descriptive
	Presence of Subretinal Fluid	Count, percentage, change from baseline	All visits	Descriptive
	Photoreceptor Layer (IS/OS Junction)	Count, percentage, change from baseline	All visits	Descriptive
	Photoreceptor Layer (ELM)	Count, percentage, change from baseline	All visits	Descriptive
	Presence of hyper-reflective foci in vitreous, intraretinal and subretinal	Count, percentage	All visits	Descriptive
	Number of hyper- reflective foci in vitreous, intraretinal and subretinal	Mean change from baseline	All visits	Descriptive
	Length of longest DRIL in line scans	Mean change from baseline	All visits	Descriptive
	Presence of ERM	Count, percentage, change from baseline	All visits	Descriptive
	Presence of VMT/VMA	Count, percentage, change from baseline	All visits	Descriptive
OCTA	Foveal avascular	Mean change from	All visits	Descriptive
		Daselline	1, 3 and 6 months following Treatment 1	Treatment effect
			1, 3 and 6 months post-cellular therapy in both arms; 12	Effect of cellular therapy over time

Table 5: OCT/OCTA Outcomes				
Modality	Outcome Measure	Parameter	Timepoints	Analyses

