13.0 APPENDIX

13.1 Simulation Results

Simulations were used to produce power curves for the independent t-test. The following plots show the power curves for using the t-test in different scenarios with varying degrees of treatment decay and period effect in the simulated data. Treatment decay is defined as the attenuation of cellular treatment, which might be observed in the immediate cellular therapy/deferred sham therapy group during Study Period 2. Period effect is defined as the effect on treatment of being in Study Period 1 versus being in Study Period 2. Estimates of participant level random effects and measurement error used in these power calculations were derived from visual acuity data in the Study of Comparative Treatments for Retinal Vein Occlusion 2 (SCORE 2)⁷.

FIGURE 1 shows the power curve when estimating treatment effect of visual acuity (i.e., difference in number of letters read) holding treatment decay and period effect at 0.

Figure 1: Power Curve for T-test

Standard deviation of the patient level random effect=15 Standard deviation of the measurement error=6.2 Treatment decay (Q)=0 Period effect (T)=0 **FIGURE 2** and **FIGURE 3** show the power of estimating treatment effect of visual acuity while introducing treatment decay and a period effect, respectively.

Figure 2: Power Curve with Differing Levels of Treatment Decay

Figure 3: Power Curve with Differing Levels of Period Effect

Figures 2 and 3 show that treatment decay and a period effect do not affect power. The overall conclusion is that power to detect a treatment effect does not approach even 70% until the treatment effect is quite large (difference of 20 letters read).

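### The SAP plans two unadjusted t-tests per continuous outcome without naming a lead, and its 20-letter power conclusion fits only one of them

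*SAP*

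**What the plan says.** SAP 7.3 (strategy item 2) plans the treatment-effect analysis "for the outcome measure on the original scale and change from baseline", and SAP 7.3.1.1 repeats it: "An independent t-test will be used to analyze the treatment effect for each continuous outcome measure on the original scale and change from baseline". The comparisons are made at months 1, 3 and 6. Protocol 7.8.2.2 makes month 6 the primary comparison but names no scale. Neither document names a lead scale or adjusts for baseline.

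The outcome tables do not fully match this text. Table 3 (visual acuity) lists "Mean, mean change" from baseline, and Table 4 (microperimetry) also lists both. The tested rows of Tables 5 to 9 list change only; Table 5, for example, gives "Mean change from baseline".

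SAP 7.3 adds: "Significance testing will use 2-sided tests with alpha=0.05". It says that power is limited and cites the Appendix for this.

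Protocol 7.8.3 says the SAP gives power for the planned method of analysing the secondary outcomes. Appendix 13.1 says "Simulations were used to produce power curves for the independent t-test", with inputs "Standard deviation of the patient level random effect=15 Standard deviation of the measurement error=6.2" taken from visual acuity data in an earlier retinal vein occlusion trial. It concludes that "power to detect a treatment effect does not approach even 70% until the treatment effect is quite large (difference of 20 letters read". Its text does not state whether the simulated outcome was the visit value or the change from baseline.

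**The concern.** The two planned tests have very different precision whenever baseline and follow-up are strongly correlated, as the Appendix inputs imply. Three problems follow.

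- One power statement cannot describe both tests. If it describes the less precise one, a reader who judges a null month-6 change in visual acuity by the Appendix will think the trial much less sensitive than its own inputs say.
- When the two tests conflict, the SAP does not say which is the signal. The trial's stated efficacy purpose is to find trends that could justify a larger study, so this choice matters and should be made before the data are seen.
- With two looks at the same outcome and visit, the chance that at least one falls below 0.05 under no effect exceeds 5%.

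**Working it through.** **Inputs.** 20 participants randomised 1:1, so 10 per arm (SAP 3.2, 3.3). Two-sided alpha 0.05 (SAP 7.3). Between-patient SD 15 and measurement-error SD 6.2 (SAP 13.1, Figure 1 notes). The text of 13.1 restates neither alpha nor sample size.

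**Model implied by the inputs.** Visit value = patient effect + independent error at each visit.

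- Original-scale SD = √(15² + 6.2²) = √263.44 = 16.23
- Change SD = √2 × 6.2 = 8.77 (the patient effect cancels)
- Baseline/month-6 correlation = 225 / 263.44 = 0.854

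**Power.** Noncentral t with 18 degrees of freedom and noncentrality d / (SD × √(2/10)).

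*Reproducing the SAP's figure, original scale.* At 20 letters the noncentrality is 20 / (16.23 × 0.447) = 2.76 and power is 74.1%. Power reaches 70% at 19.1 letters. With 9 per arm, power at 20 letters is 69.0% and the 70% point is 20.2 letters. This agrees with the Appendix's rounded threshold.

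*Same inputs, change from baseline.* At 20 letters the noncentrality is 20 / (8.77 × 0.447) = 5.10 and power is 99.8%. Power reaches 70% at 10.3 letters (10.9 with 9 per arm). The original-scale threshold is 19.06 / 10.30 = 1.85 times as large.

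ANCOVA of the visit value on arm and baseline was simulated, so that the loss from estimating the baseline slope is included.

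| Appendix inputs, 10 per arm | Original scale | Change | ANCOVA |
|---|---|---|---|
| 70% power at (letters) | 19.1 | 10.3 | 10.2 to 10.3 |
| Power at 10 letters | 26% | 67% | 68% |
| Power at 20 letters | 74% | 99.8% | 99.7% |

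**Agreement of the two planned tests** (200,000 simulated trials per setting). They give different calls at 0.05 in 53% of trials at a true 10 letters and in 26% at 20 letters. At 10 letters, power is 0.675 for change and 0.256 for the original scale, a difference of 0.419. With discordance 0.531, change alone is significant in (0.531 + 0.419)/2 = 47.5% of trials and the original scale alone in (0.531 − 0.419)/2 = 5.6%. With no effect, at least one of the two is significant in about 9.5% of trials.

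**Sensitivity to the variance model** (assumed values, not in the documents).

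Lower correlation, total SD held at 16.2:

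| Correlation | 70% point: original / change / ANCOVA (letters) | Power at 20 letters: original / change / ANCOVA |
|---|---|---|
| 0.7 | 19.1 / 14.8 / 14.0 | 74% / 92% / 94% |
| 0.5 | 19.1 / 19.1 / 17.1 | 74% / 74% / 83% |

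Larger within-patient SD, between-patient SD held at 15:

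| Within-patient SD | 70% point, change | 70% point, original scale |
|---|---|---|
| 8 | 13.3 | 20.0 |
| 10 | 16.6 | 21.2 |
| 12 | 19.9 | 22.6 |

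For the change test to need 20 letters for 70% power, the change SD would have to be about 17.0. That is an error SD of 17.0 / √2 ≈ 12.0, nearly double the Appendix's 6.2.

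**The case against.** **The plan already leans towards change.** Both documents describe the secondary outcomes as changes, the SAP subsections are titled that way, and Tables 5 to 9 list change only. That is fair, and it narrows the open choice mainly to visual acuity and microperimetry. It also makes a power statement that fits only the original scale a worse match to the plan.

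**The trial is exploratory.** SAP 3.2 plans no formal hypothesis testing, protocol 7.8.2.2 limits p-values to strength of association, and SAP 7.3 openly makes no multiplicity adjustment. The 9.5% figure is small beside the many outcomes tested at three visits. This stands, and no multiplicity correction is asked for here. But SAP 7.3 still sets a 0.05 significance level, and two conflicting results need a rule for which is reported as the signal.

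**The 10.3 letters depends on the model.** It requires that 6.2 captures all within-patient variation over six months. Anti-VEGF treatment is allowed in follow-up (protocol 7.4) and could add to it. This stands: the gap narrows at correlation 0.7 and closes at 0.5. If the sponsor doubts 6.2 as the within-patient SD, the Appendix should say so.

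**Power is limited on either scale.** True: on the Appendix inputs the change test has 23% power at 5 letters and 49% at 8. The general message survives; the 20-letter figure does not carry over to change.

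**The plots may state the scale.** Figures 1 to 3 were not visible in the copy reviewed, so their axis labels could not be checked. The wording and the SD of 15 suggest the original scale. On that reading the statement is correct for one planned test and silent on the other.

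**ANCOVA is a preference.** At correlation 0.85 it adds almost nothing to the change score, and the calculations cover visual acuity only, whereas Tables 5 to 9 include counts and areas. Both points stand. The reasons for it are one prespecified estimate, adjustment for chance baseline imbalance with 10 per arm, and less loss if the correlation is lower. For skewed counts or areas its distributional assumptions need checking, as do those of the t-tests already planned.

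**Conclusion.** The concern holds and should be fixed. No lead scale is named for the treatment-effect analysis, and the text and Tables 5 to 9 disagree on which scales are tested. On the Appendix's own inputs the 20-letter conclusion describes only the original-scale visual acuity test; for the planned change test it overstates the detectable effect by a factor of about 1.9. That factor assumes 10 per arm, two-sided 0.05, independent errors at baseline and month 6, and no between-patient variation in change. It shrinks as within-patient variation grows. No confirmatory claim or sample-size decision is affected; what is at stake is the reading of the month-6 visual acuity result.

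**What to change.** In SAP 7.3.1.1, name one lead treatment-effect analysis for the continuous outcomes that have one (Tables 3 to 9): ANCOVA of the visit value on arm and baseline value, reported as an adjusted difference with a 95% confidence interval. Let month 6 lead, in line with protocol 7.8.2.2, with months 1 and 3 supportive. Keep the original-scale and change results as descriptive, and make SAP 7.3 and 7.3.1.1 agree with Tables 5 to 9.

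In SAP 13.1, state the scale, sample size and alpha behind each power curve. Limit the conclusion to visual acuity, since no variance inputs are given for other outcomes. Show power for the original scale, change and ANCOVA at several baseline/month-6 correlations, for example 0.85, 0.7 and 0.5.

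The cost is SAP wording, a re-run of the curves and one residual degree of freedom (17 instead of 18). Baseline is already collected, so no new data are needed. If the correlation really is about 0.85, the gain over the change score is negligible and the benefit is mainly clarity.

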7.3.1.2 Effect of Cellular Therapy Over Time

The mean change from baseline at 1, 3 and 6 months post-cellular therapy will be assessed in both treatment arms. Comparisons will be made between the two arms to identify any differences in the effect of cellular therapy. If there are no statistically significant differences identified, the treatment arms will be combined, and a within-patient paired t-test will be performed. If a statistically significant difference is found, within-patient paired t-tests will be performed separately in each treatment arm to assess the effect of cellular therapy. Additionally, the effect of cellular therapy will be assessed in the immediate cellular therapy/deferred sham therapy arm at 12 months compared to the screening visit with a within-patient paired t-test.

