7.8.2.2 Efficacy

All secondary outcome analyses will follow a similar form and strategy as outlined in the SAP. Data from the study eye will be presented. Tables and graphs of each outcome and change from baseline in each outcome will accompany the results of the analyses as appropriate and will be used to visualize the trends over time. See Section 6.3.2 for a list of outcomes of interest. A (modified) intent-to-treat approach will be followed in which all participants who were randomized *and received the first injection* (cellular or sham) will be included in the analysis and analyzed in the arm to which they were randomized.

The primary analysis will be a comparison at 6 months between those who receive immediate cellular therapy vs those who receive immediate sham therapy. A t-test will be used for continuous outcomes and Fisher's exact test or an appropriate non-parametric test may be used for categorical outcomes. Comparisons at other time points prior to 6 months may also be performed.

An additional analysis will look at treatment effect duration for those who receive immediate cellular therapy and assess whether the treatment effect remains the same at 6 and 12 months or increases/decreases as time passes.

As noted in Section 6.3.2, there are many outcomes of interest within each modality. P-values calculated from the statistical tests noted above will only be used as an indication of strength of association and should not be used for hypothesis testing.

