3.2 Sample Size Considerations

There is no formal sample size calculation for this small phase I/II study and no formal hypothesis testing will be performed. A sample size of 20 participants was chosen to ensure that it is financially feasible to conduct the study and logistically possible to complete the study enrollment within the study period. The primary objective is to assess the safety and feasibility of the stem cell therapy; however, it is desired to obtain some gauge of potential efficacy of this cell therapy. Thus, participants will be randomized 1:1 to immediate cellular therapy/deferred sham or immediate sham/deferred cellular therapy. After their first treatment (cellular or sham), participants will be followed for 6 months, at which time participants who initially received sham treatment will be given stem cell treatment and vice versa. The small sample size is not ideal, but for practical purposes, it would be difficult to increase the sample size significantly without increasing the enrollment period for the study.

Although the study as designed may not be large enough to determine efficacy, some efficacy signals might be observed with the current study design. Such a signal may warrant further investigation of this therapy for CRVO. When a phase II/III randomized controlled trial is planned, appropriate sample size calculations will be performed.

It is recognized that the study has limited power to show efficacy; however, we hope to obtain some trends in change in visual function or retinal morphology or perfusion that may suggest efficacy to justify a larger randomized prospective clinical trial. Power calculations are explored in section 5.2.2 for the proposed method of analyzing the secondary outcomes.

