4.2.2 Baseline

For all visits occurring during Study Period 1, baseline will be defined based on the measurements taken prior to Treatment 1 (during the screening/baseline visits). For all visits occurring during the Study Period 2, baseline will be defined based on the measurements taken during the Month 6 visit immediately prior to Treatment 2. It is noted that for participants in the sham/deferred treatment group, these two sets of baseline measurements should be similar due to the fact that no active treatment is given during the Study Period 1. We will review the values of these two sets of baseline measures to examine the extent to which this is true.

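### SAP 7.3.1.2 reports uncontrolled before-after paired t-tests as the effect of cellular therapy, and uses a significance pre-test on about 10 versus 10 eyes to decide whether to pool the arms

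*SAP*

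**What the plan says.** SAP 7.3.1.2 takes change from baseline at 1, 3 and 6 months after cell therapy in both arms and compares the arms. It then branches: "If there are no statistically significant differences identified, the treatment arms will be combined, and a within-patient paired t-test will be performed". If the arms do differ significantly, a paired t-test is run in each. A third test is added: "the effect of cellular therapy will be assessed in the immediate cellular therapy/deferred sham therapy arm at 12 months compared to the screening visit", again paired.

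Under SAP 4.2.2 the pre-cell baseline is the screening/baseline measurement in the immediate-cell arm and the Month 6 visit in the deferred-cell arm. In SAP Table 3 the row for this analysis lists post-cell time points only. About the sham arm's two baselines, 4.2.2 adds: "We will review the values of these two sets of baseline measures to examine the extent to which this is true".

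The sham-controlled analysis is in SAP 7.3.1.1, for Period 1: "An independent t-test will be used to analyze the treatment effect for each continuous outcome measure on the original scale and change from baseline".

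SAP 7.3 says the efficacy analyses are meant "to differentiate these changes from non-treatment factors (i.e., natural course of the condition, learning or placebo effects or testing variations". On the status of the tests, SAP 7.3 states "Significance testing will use 2-sided tests with alpha=0.05", SAP 3.2 states that "no formal hypothesis testing will be performed", and Protocol 7.8.2.2 states that p-values "should not be used for hypothesis testing". Protocol 7.8.2.2 plans the 6-month comparison of the arms and a look at whether the effect lasts from 6 to 12 months. It describes neither the pooled paired test nor the pre-test.

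**The concern.** There are two faults, and the first is the larger.

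**No control.** All three tests compare the same eyes before and after cells. A non-treatment change enters the estimate in full and is reported as the effect of the cells. The SAP itself names learning, placebo response and natural course as things to be separated out. Protocol 6.1.2 concedes that masking may be hard to ensure. Protocol 7.4 allows anti-VEGF treatment during follow-up but not within four weeks of a study procedure, so its timing may differ between baseline and later visits.

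**The gate.** A non-significant difference between two groups of about 10 is taken as permission to pool. It is weak evidence that the arms agree. It also lets a p-value choose the reported analysis, although both documents disclaim hypothesis testing.

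What is at stake is the reading of the trial. SAP 3.2 hopes for trends that would justify a larger study. The pooled paired test is more precise than the randomised comparison, so it will tend to give the smaller p-value, under a label that claims a cell effect.

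**Working it through.** **Inputs from the documents**
- 20 participants randomised 1:1 (SAP 3.2, 3.3), so about 10 per arm. The split is inferred.
- Two-sided alpha 0.05 (SAP 7.3), taken also as the pre-test level. The SAP does not name the between-arm test in 7.3.1.2; a t-test is assumed.
- Visual acuity: participant SD 15, measurement-error SD 6.2 letters (SAP 13.1).

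**Assumptions**
- The participant effect cancels in a change score, so the change SD is 6.2 × √2 = 8.77. Values of 12 and 15 are also tried.
- Drift sizes are assumed, because the documents give none.
- One outcome at one time point, no dropout.

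**The plan's own figure.** SAP 13.1 says power does not approach 70% until the difference is 20 letters. The raw-score SD is √(15² + 6.2²) = 16.23. With 10 per arm, the noncentral t gives 69.7% at 19 letters and 74.1% at 20. The inputs therefore fit that statement as a rough bound. The SAP gives no operating characteristics for the 7.3.1.2 rule.

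**Precision on change from baseline**

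| Analysis | Standard error | 95% CI half-width |
|---|---|---|
| Pooled paired, n = 20 | 8.77/√20 = 1.96 | 1.96 × 2.093 = 4.1 |
| Period 1 cell versus sham, 10 v 10 | 8.77 × √(2/10) = 3.92 | 3.92 × 2.101 = 8.2 |
| Sham arm's two baselines, n = 10 | 8.77/√10 = 2.77 | 2.77 × 2.262 = 6.3 |

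The baseline review in 4.2.2 therefore cannot exclude a drift of a few letters.

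**The two-step rule with no cell effect.** Simulated trials: pre-test at 0.05, then the pooled paired test, or both single-arm paired tests. Share of trials with at least one significant result:

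| Non-treatment gain in each period | SD 8.77 | SD 12 | SD 15 |
|---|---|---|---|
| 0 letters | 8% | 8% | 8% |
| 2 letters | 19% | 14% | 12% |
| 3 letters | 33% | 21% | 17% |
| 5 letters | 69% | 45% | 32% |

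The randomised Period 1 comparison of change is significant in 5% of trials whatever the common drift. At SD 8.77 with 3 or 5 letters of drift, the paired estimate averages 3.0 or 5.0 letters and the sham-controlled estimate averages 0.

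**Gain in Period 1 only.** At SD 8.77, a gain of 2, 3 or 5 letters gives 12%, 18% or 35%.

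**Month 12 versus screening (n = 10, SD 8.77).** If 2 or 3 letters accrue in each period, 4 or 6 in total, the test is significant in 25% or 49% of trials. If only 2 or 3 letters accrue in total, it is 10% or 16%.

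**The gate.** Power to detect a true 5-letter difference between the arms is 23% at SD 8.77, 14% at SD 12 and 11% at SD 15. Arms that differ by 5 letters are thus pooled in 77%, 86% or 89% of trials. The pooled test alone, without the gate, is significant in 16%, 31% or 68% of trials at drifts of 2, 3 or 5 letters (SD 8.77). Most of the excess therefore comes from the lack of control.

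**The case against.** - **This is supportive and exploratory.** The primary outcomes are safety and feasibility. Protocol 7.8.2.2 makes the randomised 6-month comparison the main efficacy analysis and limits what p-values may be used for. This stands, and it limits how serious the point is.
- **The drift is invented and may be small.** Protocol 4.0 describes vein occlusion as typically non-progressive, eligibility requires at least 6 months of vision loss, and the SAP expects the sham arm's two baselines to be similar. This bears on natural course. It does not exclude learning or placebo response.
- **Equal drift in both periods is a harsh scenario.** Acuity is tested several times before the deferred arm's Month 6 baseline, so learning would probably come early. This stands: with a gain in Period 1 only, the rates fall to roughly half to two thirds. They remain above the 8% seen without drift.
- **The gate adds little.** Also right: 5% becomes 8% without drift, and it adds 1 to 3 points at the drifts above.
- **SAP 7.3 speaks of the efficacy analyses as a set, and 7.3.1.1 supplies the control.** That is a fair reading of the aim. But 7.3.1.2 separately says that its tests assess the effect of cellular therapy, and nothing in it refers back to the sham result.
- **Part of the remedy exists.** The planned summaries already give change by arm, period and visit, and SAP 4.2.1 notes that Period 2 is not a true sham period for those given cells first. So what remains is the gate, the label and the missing confidence intervals.

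**Conclusion.** The concern holds. As written, SAP 7.3.1.2 attributes any non-treatment change to the cells. The absence of a control follows from the text and does not depend on how large the drift is. The error rates do: at SD 8.77 with no cell effect they run from 8% without drift to 69% with 5 letters in each period. They are lower if the change SD is larger or the gain is confined to Period 1. Sham data enter only as the deferred arm's Month 6 baseline, and no test contrasts post-cell with post-sham change. The randomised Period 1 comparison and the primary outcomes are unaffected. The section should be corrected, but it does not undermine the trial.

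**What to change.** In SAP 7.3.1.2, delete the between-arm pre-test and the pooling rule. Report change at 1, 3, 6 and 12 months after cells as before-after means with 95% confidence intervals, by arm, and also combined at 1, 3 and 6 months. Title the section and its tables as change after cellular therapy, and do not present them as tests of cell effect. Show the sham arm's Period 1 change beside them. State that any claim of cell effect rests on the Period 1 cell-versus-sham comparison of change from baseline in 7.3.1.1, with its 95% confidence interval.

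A mixed model using both periods is not needed. If one is added, it should be a sensitivity analysis that states its assumptions of immediate onset and no decay. For a true 10-letter effect, a seven-visit model with visit effects and a cell-received indicator returns 4.3 letters if onset falls between months 1 and 3, and 13.6 if the effect halves in Period 2.

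The cost is SAP wording and table titles, with no new data. The real price is precision: statements about cell effect rest on a standard error of 3.92 letters instead of 1.96.
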